4.1 Informed Consent Procedures

Informed consent will be gained from all research participants. Principal investigator or the practice nurse will take consent,

Arrangements for seeking consent:

In designing the consent process, we aimed for transparency and clarity, and we chose wording that we think reduces the possibility that potential participants feel pressured to join the study due to a sense of moral responsibility.

Consent for the validity and reliability testing will be sought electronically.

Procedure for seeking consent for the feasibility testing, RCT, survey and interview: when expressions of interest are received from potential participants, we shall approach the individuals and arrange a time and format (i.e. virtual or face-to-face) that is preferred and convenient for them and in line with Covid 19 pandemic guidelines. All potential participants will be given an information sheet outlining the purpose of the project and interview and given time to reflect on the study. Help and clarification will be given as needed. During this process the nurse-researcher will make judgements whether the potential participant is able to understand the information relevant to the decision, retain that information, use or weigh up that information as part of the process of making the decision, and communicate their decision. Participants appearing to be competent will be asked to sign a consent form (electronic signature will be accepted). If any doubts arise with regards to competence, the service user's consultee will be approached, if available, or the

SU Non CTIMP Healthcare Research Protocol

decision will be postponed. The service user will not be included in the study if not competent and no consultee/representative available. Consent will be recognised as a continuously negotiated process, which provides opportunities for ongoing communication between the researcher and participant ensuring voluntary and informed participation. For consenting participants, a copy of the consent will be retained in the patient's notes, a copy will be offered to the participant and a copy will be securely stored by the researchers (chief investigator's locked office).

Participant Information Sheets (PIS):

Participant information sheets will clearly explain the study in plain language. A copy given to participants will be kept for future reference. GDPR leaflet and Summary information will be included in PIS. The date PIS has been given to the participant will be recorded in the notes along with the consent form to ensure sufficient length of time for participants to decide on their involvement.

Participants will have as long as needed to decide whether or not they want to take part, maximum of 14 days.

4.2 Screening Procedures

Initial screening will be performed by a member of the potential participant's usual clinical care team. This healthcare professional will keep a screening log record.

4.3 Randomisation Procedures (if applicable)

Randomisation of participants in Phase 2 will be performed to promote internal design validity and minimise the effects of confounding. To avoid selection bias and enable allocation concealment, GP practices will be selected and patients consented before randomization. While masking is not possible due to the design of the study, ascertainment bias will be lowered by researchers not being aware of the randomization results until after they have accessed the nursing and medical notes and elicited necessary data. Cluster randomization will allow each practice its own care as an independent entity and will minimize contamination. The cluster design has been accounted for in the sample size.

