2.2 Trial Design

Phase 1

- Validity testing: content validity index (CVI), cognitive interviews, construct validity testing
- Feasibility trial
- Reliability testing (inter-rater reliability)

Phase 2

[figure not shown]
- Randomised controlled trial (cluster group randomization by GP practice, intervention arm (ADRe Profile implementation), control arm (standard of care))

Phase 3

- Interviews and survey with participants of phase 2

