3.1 Number of Subjects and Subject Selection

Content Validity Index sample size n = 10

Participants: a convenience sample of 2 GPs, 2 pharmacists, 2 nurses working in general practice/community and 2 care assistants working in general practice/community and 2 patients

Recruitment strategy: advertise in research networks and the university

Contrast group sample size n = 2x20

Participants: a convenience sample of up to 20 service users > 64 who do not take prescribed medicines daily.

Recruitment strategy: Advertise in research networks and the university

Cognitive interview sample size n = 5

Participants: a convenience sample of 1 patient, 1 nurse working in general practice/community, 1 care assistant working in general practice/community, 1 GP + 1 pharmacist

Recruitment strategy: Advertise in research networks and the university

Inter-Rater Reliability sample size n = 20 + 30 = 50

Participants: 20 service users from 2 general practices, >64, with >4 prescribed medicines.

Recruitment strategy: Approach cluster areas in Swansea Bay UHB and Hywel Dda UHB. Invitation by letter and/or email. General practice to identify suitable patients and approach them to invite for participation.

Randomised Controlled Trial sample n = 60

Participants: 6 new general practices x 10 patients and practice / district nurses or nurse assistants

SU Non CTIMP Healthcare Research Protocol

Recruitment strategy: approach all 8 GP clusters in Swansea Bay UHB and 7 clusters in Hywel Dda UHB by post and/or email. General practice to identify suitable patients and approach them to invite for participation.

Calculation of the sample size:

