RCT (sample = 60): Previously, in a 'before and after' single arm intervention study, with participants acting as their own controls, 17/19 (89%) had improvement in at least 1 clinical problem when ADRe Profiles for polypharmacy were used (Jordan et al submitted). We hypothesised that 9/19 (47%) would have shown some improvement without intervention, necessitating an effective sample of 40 patients (20 in each arm), with 5% significance and 90% power (Uitenbroek 1997). Based on the reported intra-cluster coefficient (0.02), (Jordan et al 2015), and a design effect of 1.18, to achieve an effective sample size of 40, we need an actual sample size of 48 (Killip et al 2004). 10 patients in each of 6 clusters (GP practices) allows for 20% loss to follow up, which is realistic in general practice, where either patient or nurse may be unavailable for follow up.

Survey sample size: up to 3 nurses, 3 pharmacists, 3 GP's and up to 30 service users.

For the survey, all health professionals involved with the intervention arm (n=9) and all service users in the intervention arm (n=30) will be included. The aim is to gain stakeholder views on the intervention.

Qualitative semi-structured interviews sample size - 3 nurses, 3 pharmacists, 3 GP's and 3 service users

For the qualitative interviews, a convenience sample of 12 participants will be selected. This will include all nurses, GP's and pharmacists in the intervention arm, as well as a purposive sample of 3 patients. The patients will be selected based on the most positive and most negative responses in the survey. The aim is to gain stakeholder views on the intervention and to supplement and illustrate the RCT data.

Phase 1

- **Content validity index respondents:** healthcare professionals (current or retired, working full-time or part-time, willing to participate and sign informed consent), service users (age > 64, willing to participate)
- **Cognitive interview respondents:** healthcare professionals (current or retired, working full-time or part-time, willing to participate), service users (age > 64, willing to participate and sign informed consent)
- **Contrast group validity respondents:** group A (people, age >64, no daily prescribed medicines - vitamin and nutritional supplements and moisturising skin preparations will not be counted as 'medicines', willing to participate and sign informed consent), group B (as below)

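### With six practices to allocate, section 4.3 names no balancing method and no fixed 3:3 ratio, so chance imbalance between arms, above all at practice and health-board level, is left uncontrolled though cheap to limit

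*Combined protocol and SAP*

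**What the plan says.** Section 4.3 gives the purpose of randomisation: "Randomisation of participants in Phase 2 will be performed to promote internal design validity and minimise the effects of confounding". Section 2.2 makes the unit the practice ("cluster group randomization by GP practice"), and section 3.1 sets the number at "6 new general practices x 10 patients". The allocation ratio is not stated. It can be inferred as three practices per arm, because the survey text in 3.1 has "all service users in the intervention arm (n=30) will be included".

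On timing, 4.3 says "GP practices will be selected and patients consented before randomization". It also describes "researchers not being aware of the randomization results until after they have accessed the nursing and medical notes and elicited necessary data". Section 4.5 has the notes read in both arms at step 1. Section 8.3 lists a baseline medication list (Form 07) and a baseline Profile filled from the notes (Form 08).

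The only visible handling of imbalance is in the analysis. Section 7.1 adjusts for site and accounts for age, diagnoses and medicines' use. Section 7.5 adds GP practice and describes the regressions as exploratory.

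**The concern.** With six units, a single draw can leave the arms different in case mix, prescribing habits or health board. Each of these could affect how many problems are found and addressed. A patient with more recorded problems at baseline has more that can be addressed, so a chance difference could be mistaken for an effect of the Profile or could mask one.

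The information needed to limit this can be available in time. Patients are consented before allocation, and step 1 notes can be read before it. Section 4.3 does not say that allocation follows the notes, but its blinding condition is compatible with that order. The plan makes no use of this information when allocating.

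**Working it through.** **Inputs from the documents.** Six practices of 10 (3.1); ICC 0.02 and design effect 1.18 (3.1 and 7.4); 30 patients in the intervention arm (3.1).

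**Inputs assumed.** The outcome ICC of 0.02 also applies to baseline measures, with 0.10 as a sensitivity value. There are two independent, normally distributed baseline measures. For the board example, three practices come from each of two health boards.

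**The plan's own figure.** Design effect = 1 + (10 − 1) × 0.02 = 1.18. Then 40 × 1.18 = 47.2, which the plan takes as 48 (8 per practice × 6), and 48 / 0.8 = 60. This reproduces the step from 40 to 60. The sample size is not in dispute here.

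**Number of allocations.** C(6,3) = 20, or 10 distinct splits, each with its mirror image. If 3:3 were not enforced and each practice were allocated by coin toss, it would occur with probability 20/64 = 31%, and all six practices would fall in one arm with probability 2/64 = 3%.

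**Patient-level measures, unrestricted 3:3.** The between-arm difference D, in patient SD units, has variance (2/30) × (1 + 9 × ICC). P(|D| > 0.5) = 2 × (1 − Φ(0.5/SD)). For two measures, P(at least one) = 1 − (1 − P)².

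| Case | SD (RMS) of D | One measure > 0.5 SD | At least one of two > 0.5 SD |
|---|---|---|---|
| 60 patients randomised individually | √(2/30) = 0.26 | 5% | 10% |
| Six practices, ICC 0.02 | √(0.0667 × 1.18) = 0.28 | 7% | 14% |
| Six practices, ICC 0.10 | √(0.0667 × 1.90) = 0.36 | 16% | 29% |

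**Practice-level features.** In units of the between-practice SD, D has SD √(2/3) = 0.82. It exceeds 0.5 in 54% of draws and 1.0 in 22%.

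**Health board.** With three practices from each of two boards, 2 of 20 draws (10%) put each board wholly in one arm. If instead two of the six practices shared a board, they would fall in the same arm in 8 of 20 draws (40%).

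**Can the analysis repair it?** Each practice sits wholly in one arm, so a fixed practice effect is aliased with arm. Six clusters in two arms leave about 6 − 2 = 4 cluster-level degrees of freedom, enough for very few practice-level covariates. Patient-level covariates such as number of medicines can be adjusted for, because they also vary within practices.

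**Restricting the draw.** I ranked the 20 allocations by the summed squared differences on the two measures and drew from the best 14 (100,000 simulated sets of six practice means).

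| ICC | RMS, all 20 | RMS, best 14 | At least one > 0.5 SD, all 20 | At least one > 0.5 SD, best 14 |
|---|---|---|---|---|
| 0.02 | 0.28 | 0.21 | 14% | 2% |
| 0.10 | 0.36 | 0.27 | 29% | 11% |

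**Why 14.** Any two practices are together in 4 of the 10 splits and apart in 6. Dropping 3 splits (6 allocations) leaves at least 1 together and 3 apart, so no pair is ever locked. Dropping 4 splits can remove all 4 in which a pair is together. Keeping only the best 10 allocations locked some pair in about 56% of simulated sets.

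**The case against.** Unrestricted randomisation is valid, and chance imbalance is not bias. The wording in 4.3 is a conventional reason for randomising and does not promise exact balance. That stands. A reader might infer that the comparison is biased, or that randomisation fails; the documents do not support either.

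A reader might also infer that having six practices makes material imbalance the usual result. With a threshold of 0.25 SD, at least one of two measures exceeds it in 1 − (1 − 0.373)² = 61% of draws at ICC 0.02. Individual randomisation of 60 patients would give 1 − (1 − 0.333)² = 56%, so most of that figure reflects sample size and a low threshold.

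Sections 7.1 and 7.5 already plan adjustment for age, diagnoses and medicines' use, and before-after differences remove much of the baseline level. This weakens the concern for patient-level measures. It does not help with differences between practices. If site in 7.1 means health board (the term is not defined), board could be adjusted for, except in a draw that confounds it fully with arm.

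Finally, the RCT flow diagram is not shown and some passages were removed, so the absence of a balancing method can be asserted only for the visible text.

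**Conclusion.** The point holds as a cheap improvement to a small cluster design, not as a defect that invalidates it. For patient-level measures the extra risk from clustering is modest at ICC 0.02: 14% against 10% for a difference above 0.5 SD on at least one of two measures. It is larger at an assumed ICC of 0.10 (29%). The stronger reason to act is practice-level and board-level difference, which the planned adjustment can do little about.

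The patient-level figures rest on carrying the outcome ICC over to covariates and on two independent normal measures. The 10% board figure rests on an assumed three-and-three split; the documents do not say how many practices will come from each board. The claim that chance imbalance would simply be read as the Profile's effect goes too far, given the adjustment already planned.

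**What to change.** **In 4.3:**
- Fix the ratio at three practices per arm, and allocate all six together once patients are consented and step 1 notes are read.
- List the 20 allocations. Score each on health board, mean baseline number of problems from the notes (Form 08) and mean number of medicines (Form 07), with weights set in advance.
- Drop the 6 worst, as three mirror-image pairs, and draw one of the remaining 14 by computer. Choose weights so that an allocation confounding board fully with arm is among those dropped.

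**In 7.1 and 7.5:** add the baseline number of problems from the notes as a covariate alongside medicines' use. Form 08 supplies it in both arms, so no new data are needed.

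**Cost:**
- The sample size and patient contacts do not change, but all six practices must be ready before any is allocated, which may hold up early ones.
- The smallest possible two-sided randomisation-test p rises from 2/20 = 0.10 to 2/14 = 0.14, though the plan specifies no such test.
- The gain shown is for two measures. Scoring health board as a third factor will reduce it somewhat on the other two.

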4.5 Schedule of Assessment (in Diagrammatic Format)

Phase of study	Intervention arm	Control arm
Phase 1 - feasibility	Medical notes accessed for items to populate ADRe Profile	No control
	Self-completed ADRe Profile	
	Researcher-completed ADRe Profile	
Phase 2 – RCT step 1	Medical notes accessed for items to populate ADRe Profile	Medical notes accessed for items to populate ADRe Profile
	Self-completed ADRe Profile	Standard of care
	Nurse or researcher-completed ADRe Profile	Standard of care
Phase 2 – RCT step 2	Medical notes accessed for items to populate ADRe Profile	Medical notes accessed for items to populate ADRe Profile
	Self-completed ADRe Profile	Standard of care
	Researcher-completed ADRe Profile	Standard of care
Phase 3 – Survey and interviews	Survey administered to service user participants	
	Interviews performed with selected	

	participants (3 service users, 3 nurses, 3 GP's, 3 pharmacists)	
--	---	--

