Data will be entered into excel via the electronic version of ADRe, imported into SPSS and described for the before and after ADRe administrations. Statistical analysis: differences between before and after the intervention will be calculated for: number and nature of problems addressed, prescription regimens, and NHS use. The impact of GP practice, age, diagnoses, and medicines' use (numbers and types of medicines prescribed) will be described and accounted for in exploratory bivariate and multivariate regression analyses. To explore the recorded changes and potential for further clinical gains, putative aetiologies of service users' signs and symptoms will be ascribed, using clinical information from medical and nursing records, including, but not restricted to, information on ADRe, and the list of medications prescribed (and over the counter). The ascription will be checked by supervisors using manufacturers' literature and formularies. Juxtaposition of ADRe and medication lists will generate suggestions for changes to improve the processes and possibly the outcomes of care. The prevalence of problems on the before and after profiles will be compared with two by two contingency tables, using McNemar's test for related dichotomous variables (Altman 1991).

Survey

Data will be described using the Statistical Package for Social Sciences (SPSS) and later combined with the interview results.

Interviews and recorded ADRe consultations

All interviews (and relevant parts of ADRe consultations) will be transcribed verbatim by the researcher/professional transcriber and anonymised. Transcripts will be

SU Non CTIMP Healthcare Research Protocol

coded, categorised, analysed and interpreted alongside the data of all completed cases, to identify, analyse and report patterns within data (Braun and Clark, 2006). The transcripts will be analysed by the team using the constant comparative method which will provide a systematic, re-iterative way of comparing and contrasting emerging codes, categories and concepts and ensure that theoretical perspectives are embedded in the description of change. Two researchers ([name]) will ensure validity of the analysis and verify interpretation. Disagreements will be resolved through discussion at team meetings. Diaries/logs will also be analysed in association with interview transcripts.

Triangulation

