8.3 Case Report Form

Swansea Trials Unit's forms will be adapted for use in CRF (with permission)

1 List of ADReGP Case Report Forms

Number	Title
FORM 01	Inclusion Criteria
FORM 02	Exclusion Criteria
FORM 03	Eligibility review
FORM 04	Randomisation/Enrolment
FORM 05	Patient Details (age and gender)
FORM 06	Baseline Medical Conditions
FORM 07	Baseline Medication list
FORM 08	Baseline ADRe Profile from available medical notes
FORM 09	Baseline Self-completed ADRe Profile
FORM 10	Baseline Nurse/researcher-completed ADRe Profile
FORM 11	Endpoint Medical Conditions
FORM 12	Endpoint Medication list
FORM 13	Endpoint ADRe Profile from available medical notes
FORM 14	Endpoint Self-completed ADRe Profile
FORM 15	Endpoint Nurse/researcher-completed ADRe Profile
FORM 16	Adverse Events
FORM 17	Serious Adverse Events
FORM 18	End of Treatment
FORM 19	Details of Death
FORM 20	Consent Withdrawal
FORM 21	PI Declaration
QUESTIONNAIRES	Patient survey Nurse survey GP survey Pharmacist survey

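### Section 4.3 does not say which notes reading its masking safeguard covers; as scheduled, it protects the baseline reading but not the endpoint reading

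*Combined protocol and SAP*

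**What the plan says.** Section 4.3 concedes the general position, "While masking is not possible due to the design of the study", and then offers one protection: "ascertainment bias will be lowered by researchers not being aware of the randomization results until after they have accessed the nursing and medical notes" and have extracted the data they need. It does not identify the reading. On timing it adds that "GP practices will be selected and patients consented before randomization".

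Section 4.5 lists "Medical notes accessed for items to populate ADRe Profile" for both arms at RCT step 1 and again at RCT step 2. Section 8.3 gives each reading its own form: Form 08 at baseline, and Form 13, "Endpoint ADRe Profile from available medical notes". The intervention arm alone also has a self-completed Profile at both steps, a "Nurse or researcher-completed ADRe Profile" at step 1 and a "Researcher-completed ADRe Profile" at step 2. The control arm has standard care in those rows.

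The Phase 2 primary endpoints in section 2.1 take patient benefit from the notes and from the Profile. Section 7.5 has likely causes of signs and symptoms assigned from the records, and says: "The ascription will be checked by supervisors using manufacturers' literature and formularies". It does not say whether those supervisors are masked. Section 8.1 gives all analysis to the research team.

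**The concern.** A statement about ascertainment bias is naturally read as a statement about the outcome. The control arm has no Profile, so the clinical records are the only outcome source that both arms share, and at follow-up they are read on Form 13. Whether a free-text entry shows that a problem was addressed, had improved or was due to a medicine is a judgement. A reader who knows the arm, and may have helped deliver the intervention, can lean towards crediting it without meaning to. If the safeguard ends before that reading, a report that repeats 4.3 would suggest a protection that the endpoint data may not have.

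**Working it through.** The point is one of sequence, so the check sets the sections side by side.

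1. **When the safeguard ends.** Under 4.3 it ends when researchers learn the allocation, after reading the notes.
2. **How many readings there are.** Two per arm (4.5), recorded on Forms 08 and 13 (8.3).
3. **What happens between them, in intervention practices only.** Step 1 Profiles are completed by patients and by a nurse or researcher (4.5). Profiles are collected through the University login or by post (8.1), and data are entered through the electronic ADRe (7.5). Completed Profiles go to practice and academic pharmacists and then prescribers (1.4), and the study pharmacist reviews them (6.8).
4. **How much one Profile reveals.** Allocation is by practice, with 6 practices of 10 patients (7.4). One Profile shows the arm of all 10 patients in its practice. The intervention arm has 30 patients, so 30/10 = 3 practices. Once Profiles have come from three practices, the other three are known by elimination.
5. **Whether anyone is kept apart.** No section names a separate extractor for step 2, a masked outcome assessor, a masked analyst, or removal of ADRe references from the notes.

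Steps 1 to 5 together imply that the team knows the arms before Form 13 is filled in.

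**How exposed each outcome is**

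- *High:* problem addressed or improved, change in signs and symptoms, medicine-related cause. All need interpretation of the records.
- *Low:* prescription changes, which are a comparison of Form 07 with Form 12.

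**Illustration only.** The documents give no misreading rate, so the rates here are assumptions. Take the 47% control improvement in 7.4, assume no true effect, and let a fraction q of unimproved intervention patients be credited as improved. The recorded rate is 0.47 + 0.53q:

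- q = 0.1: 0.523, a false difference of 5.3 points
- q = 0.2: 0.576, 10.6 points
- q = 0.3: 0.629, 15.9 points

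Next, take a two-sided 5% pooled two-proportion z test with the plan's 20 effective patients per arm. For a recorded excess d, the chance of rejection is Φ((d − 1.96·se0)/se1) + Φ((−d − 1.96·se0)/se1). Here se0 is the pooled and se1 the unpooled standard error, with p = 9/19. For d = 0.10:

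- se0 = √(0.524 × 0.476 × 2/20) = 0.158
- se1 = √((0.574 × 0.426 + 0.474 × 0.526)/20) = 0.157
- the two tails are 9.1% and 0.5%, together 9.6%

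| Recorded excess d | False-positive rate |
|---|---|
| 0 | 5.0% |
| 5 points | 6.1% |
| 10 points | 9.6% |
| 15 points | 15.6% |
| 20 points | 24.4% |

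The illustration also assumes that error runs in one direction and only in the intervention arm. It shows what the assumption implies, not how large the risk is.

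**The case against.** The strongest reply is that a reader might infer that masking at step 2 is impossible, or that the protocol admits the researchers are unmasked there. It says neither. Section 4.3 does not name the reading. A nurse may complete the step 1 Profile. Section 4.5 lists step 2 notes access before the researcher's step 2 Profile. Section 4.4 has a researcher train the nurses but does not say whether that follows randomisation or is confined to one arm. The RCT flow diagram in 2.3 was not available to this review. A separate extractor would satisfy 4.3 as written. All of this stands, so knowledge of the arms at step 2 is an inference from the schedule. It remains a firm inference, because Profiles reach the team from intervention practices alone and no separation of roles is planned.

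A reader might also infer that 4.3 promises masked outcome assessment. It does not: it concedes that masking is not possible and claims only that bias is lowered. Nor are all Phase 2 endpoints equally exposed, and assigning causes is largely exploratory in 7.5.

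Baseline masking is not worthless either, since baseline values enter every before-after difference. Finally, the arms differ in data source as well as in masking, because only the intervention arm has Profile data. Masking the reading of notes does not cure that.

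**Conclusion.** The point holds as a gap in the plan. The one stated safeguard against ascertainment bias is unspecified for the endpoint reading and, as the schedule stands, protects only the baseline reading. This rests on two things: Profiles reaching the team between the readings from intervention practices only, and the absence of any named masked extractor or assessor. It bears mainly on the judgement-based outcomes.

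The size of any bias is unknown. A reader might take the 5 to 16 points in the illustration as an estimate for this trial. The documents give no basis for the 10% to 30% rates behind it, so those figures should not be used to grade the concern. The change is still worth making because it is cheap and masked judgement is hard to restore once endpoint extraction has begun.

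**What to change.** 1. **Section 4.3.** Limit the masking claim to the baseline notes, unless step 2 extraction is also masked.
2. **Form 13.** Where possible, assign extraction to an existing team member who did not train staff, complete Profiles or receive Profiles for that practice.
3. **Section 7.5, between-arm comparison.** Have the supervisors who already check the causes judge *addressed or improved* and likely cause for both arms. They should work from coded extracts of the sources both arms have (Forms 07, 08, 12 and 13), with arm and practice removed. Replace any reference to ADRe with neutral wording, and keep the clinical finding and the action taken. Deleting such entries outright could remove the events being counted and bias against the intervention.
4. **Profile data.** Report Forms 09, 10, 14 and 15 separately as within-arm results, so that the section 2.1 outcome, which uses both notes and Profile, is not changed without saying so.

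**Cost.** No new staff are needed, but supervisors move from checking causes to a wider judging task. Up to 4 forms × 60 patients = 240 forms must be coded. Some extracts may still reveal the arm, and this should be reported.
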